7. SAFETY

No inferential statistics will be performed on the safety data.

All clinical safety data will be listed by subject. Continuous variables will be summarized using n, mean, SD, median, minimum, and maximum. Frequency counts will be reported for all categorical data.

Decimal points will be presented as follows:

- n will be presented without decimal;
- Minimum/maximum in same precision as in the database;
- Mean/median in one more decimal than minimum/maximum;

- SD in one more decimal than mean/median.

Where individual data points are missing because of dropouts or other reasons, the data will be summarized based on reduced denominators.

7.1 Subject Disposition

The number of subjects enrolled, the number who completed the study, and the number who did not complete the study (overall and reasons for early withdrawal) will be tabulated by study group and overall. A listing of subjects who discontinued the study prematurely will also be presented.

7.2 Adverse Events

Adverse events will be coded (to the lowest level term) with the Medical Dictionary for Regulatory Activities (MedDRA®) version 19.0.

A study product use-emergent AE is defined as an AE that is starting or worsening at the time of or after study product administration.

AEs will be monitored and recorded from the time of the test e-vapor product trial at Screening, Visit 2 of the 12-week ALCS-RA-16-06-EV study until Week 24/EOS (or upon early termination). All events captured in the database will be listed in by-subject data listings. However, only study product use-emergent adverse events will be summarized.

Frequencies of subjects with study product use-emergent AEs, regardless of relationship to study product will be summarized by study group and sorted by system organ class. Frequencies of subjects with study product use-emergent serious adverse events will be likewise summarized. Frequencies of study product use-emergent adverse events will be summarized by severity and relationship to study group. Adverse events occurred during the product trial period will be summarized separately.

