BOPH: Biomarker of Potential Harm

eCO: Exhaled Carbon Monoxide compliance assessment

SMS: Short Message System

PFT: Pulmonary Function Test

* Baseline values reported on Day 1 (Week 1) or at Screening (for PFT only) of the 12-week ALCS-RA-16-06-EV study (CA20130) will be used.

** Visit 1 is the same as Visit 7 of the 12-week ALCS-RA-16-06-EV study (CA20130).

*** Changes in Your Health and Well-Being Questionnaire.

Test Products dispensing will occur at Visits 1, 2, 3, and 4 for the Test groups.

The expected duration of this study, from first subject, first visit (Visit 1, Week 12), through last subject, last visit will be approximately 12 weeks. The expected study duration from Screening (of the 12-week ALCS-RA-16-06-EV study) to End of Study for each individual subject is approximately 28 weeks.

Clinical safety evaluations will be performed to ensure that subjects meet the requirements of the study and to monitor subject safety. Visit 1 (Week 12, which is the same as Visit 7 of the 12-week ALCS-RA-16-06-EV study) safety evaluations will include the following: physical examination (symptom-driven); vital signs; body weight, BMI; 12-lead ECGs; clinical chemistry, hematology, and urinalysis; and pregnancy testing (all females). At Visits 2, 3, and 4, safety evaluations will include vital signs and physical examinations (symptom-driven). Visit 5/EOS (or early termination) safety evaluations will include a physical examination (symptom-driven); vital signs; body weight; BMI; 12-lead ECG; clinical chemistry, hematology, and urinalysis; and pregnancy testing (all females).

AEs will be monitored and recorded from the time of the test e-vapor product trial at Screening, Visit 2 of the 12-week ALCS-RA-16-06-EV study until Week 24/EOS (or upon early termination). Events occurring after the initial informed consent signing at Screening, Visit 1 of the 12-week ALCS-RA-16-06-EV study and before the test e-vapor product trial will be recorded and considered baseline signs and symptoms.

Any concomitant medications taken from 30 days prior to Screening, Visit 1 of the 12-week ALCS-RA-16-06-EV study through Week 24/EOS (or upon Early Termination) will also be recorded.

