4. ANALYSIS POPULATIONS

The Clinical Safety Population (CSP):

The CSP will consist of all subjects who are enrolled into this study and record at least one use of study products (i.e., conventional cigarettes or test e-vapor products) after Week 12.

The Modified Intent-to-Treat (mITT) Population:

The mITT population includes those subjects in the CSP population for which there is a baseline for a primary biomarker and at least one post-baseline biomarker measure for the primary biomarker after Week 12.

The Per-Protocol (PP) Population:

The PP population will be a subset of the mITT Population, which is comprised of subjects who completed the study without any major protocol violations, which are defined as:

- Control group: subjects who quit cigarette smoking (either by self report or NNN criteria of $\geq 80\%$ reduction in NNN from baseline at Visit 3 or 5).
- Test groups: subjects who self-report use of $> 10\%$ of baseline CPD over the course of the study*, subjects with an eCO > 8 ppm at any one visit in Visits 2 - 5, or subjects whose NNN levels are consistent with smoking cigarettes (ie, $< 80\%$ reduction in NNN from baseline) at Visit 3 or 5, and subjects who used ≤ 2 cartridges per week during any given week from Weeks 13 to 24.

*Baseline is defined as the CPD reported at Screening (Visit 2) of the 12-week ALCS-RA-16-06-EV study (CA20130), and the course of the study (post baseline) is defined as the average number of cigarettes smoked from Day 1, Week 1 of ALCS-RA-16-06-EV through the end of Week 24.

The CSP and PP populations will be used for the analyses of subject demographics, baseline characteristics and tobacco product use.

The mITT and PP populations will be used for the analyses of the primary endpoint. All other endpoints (excluding demographics, baseline characteristics, and safety data) will be analyzed based on the mITT population concept defined for each endpoint that includes subjects who has a baseline value and at least one post-baseline value. A PP population will be applied to the spirometry dataset using the criteria listed above.

The CSP will be used for the analyses of AEs, vital signs, clinical laboratory findings and other study safety related variables.

If it is determined that a subject was pregnant during the study, all of the pregnant subject's safety and biomarker data will be reported, but will be excluded from the biomarker summarization and statistical analyses.

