14.3 Safety Data Summary Tables

14.3.1 Displays of Adverse Events

Table 14.3.1.1 Adverse Event Frequency by Study Group – Number of Subjects Reporting the Event (% of Subjects Who Received Study Product) (CSP population)

Table 14.3.1.2 Adverse Event Frequency by Study Group – Number of Adverse Events (% of Total Adverse Events) (CSP population)

Table 14.3.1.3 Adverse Event Frequency by Study Group, Severity, and Relationship to Study Product – Number of Subjects Reporting Events (CSPS population)

Table 14.3.1.4 Adverse Event Frequency by Study Group, Severity, and Relationship to Study Product – Number of Adverse Events (CSP population)

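### The AE tables pool Weeks 1-12 events, counted only in subjects who went on to the extension, with extension-period events in one percentage per group

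*SAP*

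**What the plan says.** **Event window.** SAP Section 7.2 states that "AEs will be monitored and recorded from the time of the test e-vapor product trial at Screening, Visit 2" of the parent study. Section 3 gives the same window, "of the 12-week ALCS-RA-16-06-EV study until Week 24/EOS (or upon early termination").

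**Events tabulated.** Section 7.2 adds: "However, only study product use-emergent adverse events will be summarized". The definition is: "A study product use-emergent AE is defined as an AE that is starting or worsening at the time of or after study product administration". It mentions neither Week 12 nor the extension's Visit 1.

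**Period split off.** There is one: "Adverse events occurred during the product trial period will be summarized separately".

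**Population.** Section 4 says: "The CSP will be used for the analyses of AEs, vital signs, clinical laboratory findings and other study safety related variables". It also says: "The CSP will consist of all subjects who are enrolled into this study and record at least one use of study products", with that use occurring after Week 12. Section 3 adds that those invited had finished the parent study, complied with it and still met its entry criteria.

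**Denominator.** The title of Table 14.3.1.1 in Section 14.3.1 reads: "Number of Subjects Reporting the Event (% of Subjects Who Received Study Product) (CSP population").

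**The concern.** The event window opens before Week 1, but the population is fixed by what happened up to and after Week 12. A subject whose AE led to leaving in Week 3 is absent from both numerator and denominator. A subject who had the same AE in Week 3 and carried on is counted. Weeks 1-12 are thus observed only in people already known to have tolerated and followed the regimen, and their events are added to extension events in a single figure.

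Safety in this study is descriptive, so these group percentages are what readers will compare. If AEs affected continuation differently by arm, part of any contrast would reflect who stayed and not what the products did. Even with no such difference, the pooled figure is neither the AE experience of the extension nor that of everyone randomised, and nothing in the table tells the reader so.

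**Working it through.** **1. The plan's own figure.** Section 3 gives Control 52, Test 1 50 and Test 2 48. Their sum is 52 + 50 + 48 = 150, which matches the stated total enrolled. This is the most the CSP can contain. The SAP gives no parent-study group sizes, no Weeks 1-12 drop-out and no AE rates.

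**2. Following the text for three subjects.**

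| Subject | Use-emergent under 7.2? | In the CSP under 4? | Counted? |
|---|---|---|---|
| AE in Week 3, leaves the parent study | Yes | No | No |
| AE in Week 3, continues and uses product after Week 12 | Yes | Yes | Yes |
| First AE in Week 15 | Yes | Yes | Yes |

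The second and third subjects fall in the same cell of Table 14.3.1.1. No table title in Section 14.3.1 and no AE shell in Section 10 separates them.

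**3. What the selection can do to Weeks 1-12 incidence.** Let p be the true incidence in all randomised subjects of an arm. Let d1 and d0 be the probabilities of not entering the extension for subjects with and without an AE. Among those who enter, the proportion with an AE is

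p(1 − d1) / [p(1 − d1) + (1 − p)(1 − d0)].

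All values below are assumptions; none comes from the SAP. With p = 30%:

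| d1 | d0 | Calculation | Shown in continuers | Shift (points) |
|---|---|---|---|---|
| 20% | 20% | 0.24 / (0.24 + 0.56) | 30.0% | 0 |
| 30% | 20% | 0.21 / (0.21 + 0.56) | 27.3% | −2.7 |
| 40% | 20% | 0.18 / (0.18 + 0.56) | 24.3% | −5.7 |
| 60% | 20% | 0.12 / (0.12 + 0.56) | 17.6% | −12.4 |
| 80% | 40% | 0.06 / (0.06 + 0.42) | 12.5% | −17.5 |
| 20% | 30% | 0.24 / (0.24 + 0.49) | 32.9% | +2.9 |

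The sign depends only on whether d1 exceeds d0. For d1 = 40% and d0 = 20%, a true 10% appears as 7.7% and a true 50% as 42.9%.

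**4. From Weeks 1-12 to the pooled figure.** The table counts each subject once over the whole window, so the shift is diluted. If a proportion q has an AE after Week 12, independently of the first period, the pooled proportion is 1 − (1 − x)(1 − q), where x is the Weeks 1-12 proportion, and the shift is multiplied by (1 − q). At an assumed q = 30%, x = 30.0% gives 1 − 0.700 × 0.7 = 51.0%, and x = 24.3% gives 1 − 0.757 × 0.7 = 47.0%. The 5.7-point shift becomes about 4.0 points.

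**The case against.** **The window may not be meant to open in the parent study.** The sentence in Section 7.2 that sets the dates concerns recording, and all recorded events go to the listings. Product administration in the use-emergent definition could mean the extension's product. The product-trial row in the shells for Tables 14.3.1.3 and 14.3.1.4 is weak evidence either way: Section 10 warns that shells may not fit the study in every respect, and people who attended only the product trial cannot be in the CSP. This stands in part, since the SAP nowhere says outright that the tables start at parent Week 1. But nothing excludes earlier events, and a programmer following the text would include them.

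**The direction of bias is not documented.** This stands in full. A reader might infer that Weeks 1-12 incidence is understated and that the test products benefit, because new e-vapor users would leave for tolerability more often than continuing smokers. The SAP has no withdrawal counts, reasons or AE rates by arm. The enrolment figures look suggestive, with 50 and 48 against limits of 100 per test group and 52 against 50 in Control. They do not settle it: parent group sizes are not given, and entry also depended on compliance and continued eligibility, which need not relate to AEs.

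**Onset dates are listed and safety is descriptive.** Both are true. The shell for Appendix 16.2.7.1 carries onset date and time, so a reader could rebuild the split by hand. That makes the change cheap; it does not correct the summary table.

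**Restricting to events after Week 12 does not make the comparison unbiased.** Correct. Every CSP member was selected on 12 weeks of completion and compliance, so AE-prone leavers are missing from the extension period as well.

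**Conclusion.** The mismatch between window and population is on the face of Sections 4 and 7.2. Read as written, the AE tables pool two periods, the first of which is seen only in continuers. That part needs no assumption about rates.

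Understatement of Weeks 1-12 incidence is conditional. It occurs in any arm where subjects with AEs were less likely to enter the extension. It vanishes if entry was unrelated to AEs, and it reverses if subjects with AEs were more likely to enter. Over the assumed values at 30% true incidence, the Weeks 1-12 shift runs from −17.5 to +2.9 points, and it is smaller in the pooled Weeks 1-24 figure. If AEs drove leaving in one arm only (40% against 20%) and not in the other, equal true rates of 30% would appear as 24.3% and 30.0%. The SAP does not show that this happened, or in which arm.

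The primary biomarker analyses are not affected by this point. It is worth correcting because it changes what the main safety table reports.

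**What to change.** 1. In Section 7.2, define the events for Tables 14.3.1.1-14.3.1.4 as those starting or worsening after the extension's Visit 1 (Week 12), in the CSP.
2. Show Weeks 1-12 events in a separate column, footnoted as restricted to parent-study completers who continued into the extension. Keep the product trial separate, as now.
3. State in Section 7.2 and in the table footnotes that both columns describe a population selected on 12 weeks of completion and compliance, and that neither estimates incidence in all randomised subjects.

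This separates and labels the selection; it does not remove it. The cost is one onset-period flag derived from dates already collected, an added shell column, and a few lines of SAP text. No new data are needed.

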7.3 Clinical Laboratory

Clinical laboratory evaluations (clinical chemistry, hematology, and urinalysis) will be performed Visit 1 and at End-of-Study or Early Termination.

Descriptive statistics will be reported for numeric clinical data by study group and time point. Normal ranges will be listed by site.

Out of normal range and clinically significant laboratory values will be listed by subject.

Urine pregnancy tests will be completed at each study visit, and the results will be listed as “Negative” or “Positive.”

7.4 Vital Signs

Vital signs (respiration rate, pulse rate, blood pressure, and oral temperature) will be measured at each study visit, and at the End-of-Study or upon Early Termination. At these study visits, vital signs will be taken in the sitting position after at least 5 minutes of rest and at least 15 minutes after the last conventional cigarette smoked or test e-Vapor product used.

Descriptive statistics will be reported for vital sign measurements (blood pressure, pulse, respiration, and temperature) by study group and time point. Post randomization rechecks will not be used for calculation of descriptive statistics. Subjects only enrolled in the product trial period will be summarized separately.

7.5 ECG

A 12-lead ECG will be obtained at Visit 1 and at End of Study or Early Termination.

Descriptive statistics will be reported for ECG measurements (HR, PR, QRS, QT, and QTcB intervals) by study group and time point. ECG information will be listed by subject.

7.6 Concomitant Medications

All concomitant medications recorded during the study will be coded using the WHO Drug Dictionary version 01SEP2016 and listed by subject.

7.7 Physical Examination

Physical examinations will be performed at Screening. A brief physical examination (symptom driven) may be performed at each study visit, and at End of Study (or Early Termination). Physical examinations will be listed by subject and time point of collection. Changes in physical examinations (if any) will be described in the text of the final report.

8. SUMMARY TABLES AND FIGURES

Summary tables and figures are numbered following the International Conference on Harmonization (ICH) structure. Please note that all summary tables and figures will be generated using SAS® Version 9.3 or higher.

The following is a list of table numbers and titles that will be included as summary tables:

14.1 Demographic Data Summary Tables

Table 14.1.1 Summary of Disposition Overall and by Study Group (CSP, mITT, and PP population)

| | |
|--------------|---|
| Table 14.1.2 | Demographic Summary Overall and by Study Group (CSP, mITT, and PP population) |
| Table 14.1.3 | Smoking History Overall and by Study Group (CSP, mITT, and PP population) |

14.2 Data Summary Tables and Figures for Biomarkers of Potential Harm and Exposure, Product Use, Spirometry, and Questionnaire Responses

14.2.1 Biomarkers of Potential Harm and Exposure Tables

Primary and Secondary Biomarker endpoints (WBC count, HDL-C, urine 8-epi-prostaglandin F_{2α}, urine 11-dehydrothromboxane B₂, sICAM-1, total NNAL, COHb)

Whole Blood WBC Count Tables

| | |
|--------------------|--|
| Table 14.2.1.1.1.1 | Summary of Whole Blood WBC Count ($\times 10^3/\mu\text{L}$) by Study Group and Visit (mITT Population) |
| Table 14.2.1.1.1.2 | Summary of Whole Blood WBC Count ($\times 10^3/\mu\text{L}$) by Study Group and Visit (PP Population) |
| Table 14.2.1.1.2.1 | Summary of Whole Blood WBC Count Absolute Change From Baseline ($\times 10^3/\mu\text{L}$) by Study Group and Visit (mITT Population) |
| Table 14.2.1.1.2.2 | Summary of Whole Blood WBC Count Absolute Change From Baseline ($\times 10^3/\mu\text{L}$) by Study Group and Visit (PP Population) |
| Table 14.2.1.1.3.1 | Summary of Whole Blood WBC Count Percent Change From Baseline (%) by Study Group and Visit (mITT Population) |
| Table 14.2.1.1.3.2 | Summary of Whole Blood WBC Count Percent Change From Baseline (%) by Study Group and Visit (PP Population) |
| Table 14.2.1.1.4.1 | Statistical Summary of Whole Blood WBC Count Absolute Change From Baseline ($\times 10^3/\mu\text{L}$) by Study Group and Visit (mITT Population) |
| Table 14.2.1.1.4.2 | Statistical Comparisons of Whole Blood WBC Count Absolute Change From Baseline ($\times 10^3/\mu\text{L}$) Between Study Groups by Visit (mITT Population) |
| Table 14.2.1.1.5.1 | Statistical Summary of Whole Blood WBC Count Absolute Change From Baseline to Visit 5 ($\times 10^3/\mu\text{L}$) by Study Group (PP Population) |

| | |
|--------------------|--|
| Table 14.2.1.1.5.2 | Statistical Comparisons of Whole Blood WBC Count Absolute Change From Baseline to Visit 5 (x 10 ³ /µL) Between Study Groups (PP Population) |
| Table 14.2.1.1.6.1 | Summary of Whole Blood WBC Count Absolute Change From Baseline to Visit 5 (x 10 ³ /µL) by Study Group and Gender (mITT Population) |
| Table 14.2.1.1.6.2 | Summary of Whole Blood WBC Count Absolute Change From Baseline to Visit 5 (x 10 ³ /µL) by Study Group and Age Class (mITT Population) |
| Table 14.2.1.1.6.3 | Summary of Whole Blood WBC Count Absolute Change From Baseline to Visit 5 (x 10 ³ /µL) by Study Group and BMI Class (mITT Population) |
| Table 14.2.1.1.7.1 | Statistical Summary of Whole Blood WBC Count Absolute Change From Baseline to Visit 5 (x 10 ³ /µL) by Study Group and Gender (mITT Population) (Note: This analysis will only be performed if gender term is statistically significant) |
| Table 14.2.1.1.7.2 | Statistical Comparisons of Whole Blood WBC Count Absolute Change From Baseline to Visit 5 (x 10 ³ /µL) Between Study Groups by Gender (mITT Population) (Note: This analysis will only be performed if gender is statistically significant) |
| Table 14.2.1.1.8.1 | Statistical Summary of Whole Blood WBC Count Absolute Change From Baseline to Visit 5 (x 10 ³ /µL) by Study Group and Age Class (mITT Population) (Note: This analysis will only be performed if Age Class is statistically significant) |
| Table 14.2.1.1.8.2 | Statistical Comparisons of Whole Blood WBC Count Absolute Change From Baseline to Visit 5 (x 10 ³ /µL) Between Study Groups by Age Class (mITT Population) (Note: This analysis will only be performed if Age Class is statistically significant) |
| Table 14.2.1.1.9.1 | Statistical Summary of Whole Blood WBC Count Absolute Change From Baseline to Visit 5 (x 10 ³ /µL) by Study Group and BMI Class (mITT Population) (Note: This analysis will only be performed if BMI Class is statistically significant) |
| Table 14.2.1.1.9.2 | Statistical Comparisons of Whole Blood WBC Count Absolute Change From Baseline to Visit 5 (x 10 ³ /µL) Between Study Groups by BMI Class (mITT |

Population) (Note: This analysis will only be performed if BMI Class is statistically significant)

Table 14.2.1.1.10.1 Statistical Summary of Whole Blood WBC Count Absolute Change From Baseline to Visit 5 ($\times 10^3/\mu\text{L}$) by Study Group (mITT Population with Imputation of Missing Data Using Last Observation Carried Forward Method)

Table 14.2.1.1.10.2 Statistical Comparisons of Whole Blood WBC Count Absolute Change From Baseline to Visit 5 ($\times 10^3/\mu\text{L}$) Study Groups (mITT Population with Imputation of Missing Data Using Last Observation Carried Forward Method)

Table 14.2.1.1.11.1 Summary of Whole Blood WBC Count Absolute Change From Baseline ($\times 10^3/\mu\text{L}$) by Study Group and Visit (mITT Population with Outliers Excluded)

Table 14.2.1.1.11.2 Statistical Summary of Whole Blood WBC Count Absolute Change From Baseline to Visit 5 ($\times 10^3/\mu\text{L}$) by Study Group (mITT Population with Outliers Excluded)

Table 14.2.1.1.11.3 Statistical Comparisons of Whole Blood WBC Count Absolute Change From Baseline to Visit 5 ($\times 10^3/\mu\text{L}$) Between Study Groups (mITT Population with Outliers Excluded)

Table 14.2.1.1.12.1 Statistical Summary of Whole Blood WBC Count Absolute Change From Baseline to Visit 5 ($\times 10^3/\mu\text{L}$) by Study Group (mITT Population with BLQ values set to the LLOQ) (Note: This analysis will only be performed if the percentage of values that are BLQ is greater than 5% of observations.)

Table 14.2.1.1.12.2 Statistical Comparisons of Whole Blood WBC Count Absolute Change From Baseline to Visit 5 ($\times 10^3/\mu\text{L}$) Between Study Groups (mITT Population with BLQ values set to the LLOQ) (Note: This analysis will only be performed if the percentage of values that are BLQ is greater than 5% of observations.)

Serum HDL-C Tables

Table 14.2.1.2.1.1 Summary of Serum HDL-C (mg/dL) by Study Group and Visit (mITT Population)

Table 14.2.1.2.1.2 Summary of Serum HDL-C (mg/dL) by Study Group and Visit (PP Population)

| | |
|--------------------|--|
| Table 14.2.1.2.2.1 | Summary of Serum HDL-C Absolute Change From Baseline (mg/dL) by Study Group and Visit (mITT Population) |
| Table 14.2.1.2.2.2 | Summary of Serum HDL-C Absolute Change From Baseline (mg/dL) by Study Group and Visit (PP Population) |
| Table 14.2.1.2.3.1 | Summary of Serum HDL-C Percent Change From Baseline (%) by Study Group and Visit (mITT Population) |
| Table 14.2.1.2.3.2 | Summary of Serum HDL-C Percent Change From Baseline (%) by Study Group and Visit (PP Population) |
| Table 14.2.1.2.4.1 | Statistical Summary of Serum HDL-C Absolute Change From Baseline (mg/dL) by Study Group and Visit (mITT Population) |
| Table 14.2.1.2.4.2 | Statistical Comparisons of Serum HDL-C Absolute Change From Baseline (mg/dL) Between Study Groups by Visit (mITT Population) |
| Table 14.2.1.2.5.1 | Statistical Summary of Serum HDL-C Absolute Change From Baseline to Visit 5 (mg/dL) by Study Group (PP Population) |
| Table 14.2.1.2.5.2 | Statistical Comparisons of Serum HDL-C Absolute Change From Baseline to Visit 5 (mg/dL) Between Study Groups (PP Population) |
| Table 14.2.1.2.6.1 | Summary of Serum HDL-C Absolute Change From Baseline to Visit 5 (mg/dL) by Study Group and Gender (mITT Population) |
| Table 14.2.1.2.6.2 | Summary of Serum HDL-C Absolute Change From Baseline to Visit 5 (mg/dL) by Study Group and Age Class (mITT Population) |
| Table 14.2.1.2.6.3 | Summary of Serum HDL-C Absolute Change From Baseline to Visit 5 (mg/dL) by Study Group and BMI Class (mITT Population) |
| Table 14.2.1.2.7.1 | Statistical Summary of Serum HDL-C Absolute Change From Baseline to Visit 5 (mg/dL) by Study Group and Gender (mITT Population) (Note: This analysis will only be performed if gender term is statistically significant) |
| Table 14.2.1.2.7.2 | Statistical Comparisons of Serum HDL-C Absolute Change From Baseline to Visit 5 (mg/dL) Between Study Groups by Gender (mITT Population) (Note: This |

analysis will only be performed if the gender term is statistically significant)

Table 14.2.1.2.8.1

Statistical Summary of Serum HDL-C Absolute Change From Baseline to Visit 5 (mg/dL) by Study Group and Age Class (mITT Population) (Note: This analysis will only be performed if the Age class term is statistically significant)

Table 14.2.1.2.8.2

Statistical Comparisons of Serum HDL-C Absolute Change From Baseline to Visit 5 (mg/dL) Between Study Groups by Age Class (mITT Population) (Note: This analysis will only be performed if the Age Class interaction is statistically significant)

Table 14.2.1.2.9.1

Statistical Summary of Serum HDL-C Absolute Change From Baseline to Visit 5 (mg/dL) by Study Group and BMI Class (mITT Population) (Note: This analysis will only be performed if the BMI class term is statistically significant)

Table 14.2.1.2.9.2

Statistical Comparisons of Serum HDL-C Absolute Change From Baseline to Visit 5 (mg/dL) Between Study Groups by BMI Class (mITT Population) (Note: This analysis will only be performed if the BMI Class interaction is statistically significant)

Table 14.2.1.2.10.1

Statistical Summary of Serum HDL-C Absolute Change From Baseline (mg/dL) to Visit 5 by Study Group (mITT Population with Imputation of Missing Data Using Last Observation Carried Forward Method)

Table 14.2.1.2.10.2

Statistical Comparisons of Serum HDL-C Absolute Change From Baseline to Visit 5 (mg/dL) Between Study Groups (mITT Population with Imputation of Missing Data Using Last Observation Carried Forward Method)

Table 14.2.1.2.11.1

Summary of Serum HDL-C Absolute Change From Baseline (mg/dL) by Study Group and Visit (mITT Population with Outliers Excluded)

Table 14.2.1.2.11.2

Statistical Summary of Serum HDL-C Absolute Change From Baseline to Visit 5 (mg/dL) by Study Group (mITT Population with Outliers Excluded)

Table 14.2.1.2.11.3

Statistical Comparisons of Serum HDL-C Absolute Change From Baseline to Visit 5 (mg/dL) Between Study Groups (mITT Population with Outliers Excluded)

| | |
|---------------------|--|
| Table 14.2.1.2.12.1 | Statistical Summary of Serum HDL-C Absolute Change From Baseline to Visit 5 (mg/dL) by Study Group (mITT Population with BLQ values set to the LLOQ) (Note: This analysis will only be performed if the percentage of values that are BLQ is greater than 5% of observations.) |
| Table 14.2.1.2.12.2 | Statistical Comparisons of Serum HDL-C Absolute Change From Baseline to Visit 5 (mg/dL) Between Study Groups (mITT Population with BLQ values set to the LLOQ) (Note: This analysis will only be performed if the percentage of values that are BLQ is greater than 5% of observations.) |

Urine 8-epi-prostaglandin F2 α Tables

| | |
|--------------------|--|
| Table 14.2.1.3.1.1 | Summary of Urine 8-epi-prostaglandin F2 α (ng/g Cr) by Study Group and Visit (mITT Population) |
| Table 14.2.1.3.1.2 | Summary of Urine 8-epi-prostaglandin F2 α (ng/g Cr) by Study Group and Visit (PP Population) |
| Table 14.2.1.3.2.1 | Summary of Urine 8-epi-prostaglandin F2 α Absolute Change From Baseline (ng/g Cr) by Study Group and Visit (mITT Population) |
| Table 14.2.1.3.2.2 | Summary of Urine 8-epi-prostaglandin F2 α Absolute Change From Baseline (ng/g Cr) by Study Group and Visit (PP Population) |
| Table 14.2.1.3.3.1 | Summary of Urine 8-epi-prostaglandin F2 α Percent Change From Baseline (%) by Study Group and Visit (mITT Population) |
| Table 14.2.1.3.3.2 | Summary of Urine 8-epi-prostaglandin F2 α Percent Change From Baseline (%) by Study Group and Visit (PP Population) |
| Table 14.2.1.3.4.1 | Statistical Summary of Urine 8-epi-prostaglandin F2 α Absolute Change From Baseline (ng/g Cr) by Study Group and Visit (mITT Population) |
| Table 14.2.1.3.4.2 | Statistical Comparisons of Urine 8-epi-prostaglandin F2 α Absolute Change From Baseline (ng/g Cr) Between Study Groups by Visit (mITT Population) |
| Table 14.2.1.3.5.1 | Statistical Summary of Urine 8-epi-prostaglandin F2 α Absolute Change From Baseline to Visit 5 (ng/g Cr) by Study Group (PP Population) |

| | |
|--------------------|---|
| Table 14.2.1.3.5.2 | Statistical Comparisons of Urine 8-epi-prostaglandin F2 α Absolute Change From Baseline to Visit 5 (ng/g Cr) Between Study Groups (PP Population) |
| Table 14.2.1.3.6.1 | Summary of Urine 8-epi-prostaglandin F2 α Absolute Change From Baseline to Visit 5 (ng/g Cr) by Study Group and Gender (mITT Population) |
| Table 14.2.1.3.6.2 | Summary of Urine 8-epi-prostaglandin F2 α Absolute Change From Baseline to Visit 5 (ng/g Cr) by Study Group and Age Class (mITT Population) |
| Table 14.2.1.3.6.3 | Summary of Urine 8-epi-prostaglandin F2 α Absolute Change From Baseline to Visit 5 (ng/g Cr) by Study Group and BMI Class (mITT Population) |
| Table 14.2.1.3.7.1 | Statistical Summary of Urine 8-epi-prostaglandin F2 α Absolute Change From Baseline to Visit 5 (ng/g Cr) by Study Group and Gender (mITT Population) (Note: This analysis will only be performed if gender term is statistically significant) |
| Table 14.2.1.3.7.2 | Statistical Comparisons of Urine 8-epi-prostaglandin F2 α Absolute Change From Baseline to Visit 5 (ng/g Cr) Between Study Groups by Gender (mITT Population) (Note: This analysis will only be performed if the gender term is statistically significant) |
| Table 14.2.1.3.8.1 | Statistical Summary of Urine 8-epi-prostaglandin F2 α Absolute Change From Baseline to Visit 5 (ng/g Cr) by Study Group and Age Class (mITT Population) (Note: This analysis will only be performed if the Age class term is statistically significant) |
| Table 14.2.1.3.8.2 | Statistical Comparisons of Urine 8-epi-prostaglandin F2 α Absolute Change From Baseline to Visit 5 (ng/g Cr) Between Study Groups by Age Class (mITT Population) (Note: This analysis will only be performed if the Age class term is statistically significant) |
| Table 14.2.1.3.9.1 | Statistical Summary of Urine 8-epi-prostaglandin F2 α Absolute Change From Baseline to Visit 5 (ng/g Cr) by Study Group and BMI Class (mITT Population) (Note: This analysis will only be performed if the BMI class term is statistically significant) |
| Table 14.2.1.3.9.2 | Statistical Comparisons of Urine 8-epi-prostaglandin F2 α Absolute Change From Baseline to Visit 5 (ng/g Cr) Between Study Groups by BMI Class (mITT |

Population) (Note: This analysis will only be performed if the BMI class term is statistically significant)

Table 14.2.1.3.10.1 Statistical Summary of Urine 8-epi-prostaglandin F_{2α} Absolute Change From Baseline to Visit 5 (ng/g Cr) by Study Group (mITT Population with Imputation of Missing Data Using Last Observation Carried Forward Method)

Table 14.2.1.3.10.2 Statistical Comparisons of Urine 8-epi-prostaglandin F_{2α} Absolute Change From Baseline to Visit 5 (ng/g Cr) Between Study Groups (mITT Population with Imputation of Missing Data Using Last Observation Carried Forward Method)

Table 14.2.1.3.11.1 Summary of Urine 8-epi-prostaglandin F_{2α} Absolute Change From Baseline (ng/g Cr) by Study Group and Visit (mITT Population with Outliers Excluded)

Table 14.2.1.3.11.2 Statistical Summary of Urine 8-epi-prostaglandin F_{2α} Absolute Change From Baseline to Visit 5 (ng/g Cr) by Study Group (mITT Population with Outliers Excluded)

Table 14.2.1.3.11.3 Statistical Comparisons of Urine 8-epi-prostaglandin F_{2α} Absolute Change From Baseline to Visit 5 (ng/g Cr) Between Study Groups (mITT Population with Outliers Excluded)

Table 14.2.1.3.12.1 Statistical Summary of Urine 8-epi-prostaglandin F_{2α} Absolute Change From Baseline to Visit 5 (ng/g Cr) by Study Group (mITT Population with BLQ values set to the LLOQ) (Note: This analysis will only be performed if the percentage of values that are BLQ is greater than 5% of observations.)

Table 14.2.1.3.12.2 Statistical Comparisons of Urine 8-epi-prostaglandin F_{2α} Absolute Change From Baseline to Visit 5 (ng/g Cr) Between Study Groups (mITT Population with BLQ values set to the LLOQ) (Note: This analysis will only be performed if the percentage of values that are BLQ is greater than 5% of observations.)

Urine 11-dehydrothromboxane B₂ Tables

Table 14.2.1.4.1.1 Summary of Urine 11-dehydrothromboxane B₂ (ng/g Cr) by Study Group and Visit (mITT Population)

Table 14.2.1.4.1.2 Summary of Urine 11-dehydrothromboxane B₂ (ng/g Cr) by Study Group and Visit (PP Population)

| | |
|--------------------|---|
| Table 14.2.1.4.2.1 | Summary of Urine 11-dehydrothromboxane B ₂ Absolute Change From Baseline (ng/g Cr) by Study Group and Visit (mITT Population) |
| Table 14.2.1.4.2.2 | Summary of Urine 11-dehydrothromboxane B ₂ Absolute Change From Baseline (ng/g Cr) by Study Group and Visit (PP Population) |
| Table 14.2.1.4.3.1 | Summary of Urine 11-dehydrothromboxane B ₂ Percent Change From Baseline (%) by Study Group and Visit (mITT Population) |
| Table 14.2.1.4.3.2 | Summary of Urine 11-dehydrothromboxane B ₂ Percent Change From Baseline (%) by Study Group and Visit (PP Population) |
| Table 14.2.1.4.4.1 | Statistical Summary of Urine 11-dehydrothromboxane B ₂ Absolute Change From Baseline (ng/g Cr) by Study Group and Visit (mITT Population) |
| Table 14.2.1.4.4.2 | Statistical Comparisons of Urine 11-dehydrothromboxane B ₂ Absolute Change From Baseline (ng/g Cr) Between Study Groups by Visit (mITT Population) |
| Table 14.2.1.4.5.1 | Statistical Summary of Urine 11-dehydrothromboxane B ₂ Absolute Change From Baseline to Visit 5 (ng/g Cr) by Study Group (PP Population) |
| Table 14.2.1.4.5.2 | Statistical Comparisons of Urine 11-dehydrothromboxane B ₂ Absolute Change From Baseline to Visit 5 (ng/g Cr) Between Study Groups (PP Population) |
| Table 14.2.1.4.6.1 | Summary of Urine 11-dehydrothromboxane B ₂ Absolute Change From Baseline to Visit 5 (ng/g Cr) by Study Group and Gender (mITT Population) |
| Table 14.2.1.4.6.2 | Summary of Urine 11-dehydrothromboxane B ₂ Absolute Change From Baseline to Visit 5 (ng/g Cr) by Study Group and Age Class (mITT Population) |
| Table 14.2.1.4.6.3 | Summary of Urine 11-dehydrothromboxane B ₂ Absolute Change From Baseline to Visit 5 (ng/g Cr) by Study Group and BMI Class (mITT Population) |
| Table 14.2.1.4.7.1 | Statistical Summary of Urine 11-dehydrothromboxane B ₂ Absolute Change From Baseline to Visit 5 (ng/g Cr) by Study Group and Gender (mITT Population) (Note: |

This analysis will only be performed if gender term is statistically significant)

Table 14.2.1.4.7.2

Statistical Comparisons of Urine 11-dehydrothromboxane B₂ Absolute Change From Baseline to Visit 5 (ng/g Cr) Between Study Groups by Gender (mITT Population) (Note: This analysis will only be performed if the gender term is statistically significant)

Table 14.2.1.4.8.1

Statistical Summary of Urine 11-dehydrothromboxane B₂ Absolute Change From Baseline to Visit 5 (ng/g Cr) by Study Group and Age Class (mITT Population) (Note: This analysis will only be performed if the Age class term is statistically significant)

Table 14.2.1.4.8.2

Statistical Comparisons of Urine 11-dehydrothromboxane B₂ Absolute Change From Baseline to Visit 5 (ng/g Cr) Between Study Groups by Age Class (mITT Population) (Note: This analysis will only be performed if the Age class term is statistically significant)

Table 14.2.1.4.9.1

Statistical Summary of Urine 11-dehydrothromboxane B₂ Absolute Change From Baseline to Visit 5 (ng/g Cr) by Study Group and BMI Class (mITT Population) (Note: This analysis will only be performed if the BMI class term is statistically significant)

Table 14.2.1.4.9.2

